8.2.3.2. Adverse Events

- **All adverse events**

The number and proportion of patients with adverse events will be tabulated by SOC and PT.

- **Adverse events by serious/non-serious**

The number and proportion of patients with serious adverse events will be tabulated by SOC and PT. The same tabulation will be performed for non-serious adverse events.

8.2.3.3. Other Endpoints

- **Laboratory test values**

In patients with hepatic toxicity, an adverse drug reaction considered as a major investigation item, summary statistics of the values of laboratory parameters related to hepatic function (AST, ALT, Al-P, and γ -GTP) at the initiation of treatment, the onset of the adverse drug reaction, and the completion of treatment will be calculated by intervention (change in treatment with Vfend). A1.1 Definition of Visit Timing of Appendix 10.1 will be followed for values at the initiation and completion of treatment. The value immediately before the

day of onset of adverse drug reaction after the day of initiation of Vfend treatment will be used as the value at onset.

8.2.3.4. Subgroup Analysis

The number and proportion of patients who experienced at least one adverse drug reaction will be tabulated for each factor specified in Section 5.4. To evaluate the relationship between patient background factors and the development of adverse drug reactions, the analysis specified in Section 8.1.3 will be performed. The same analysis will be performed for serious adverse drug reactions.

The listing of adverse drug reactions will be prepared for contraindicated patients. The number and proportion of patients with adverse drug reactions will be tabulated by SOC and PT as necessary.

8.2.3.5. Exploratory Analysis

The following exploratory analysis will be performed for factors affecting safety.

- The number and proportion of patients with adverse drug reactions will be tabulated by SOC and PT by factor with a risk ratio of ≥ 2 or ≤ 0.5 .

An additional analysis may be performed as necessary. The exploratory analysis will be reported only when results giving important interpretation are obtained.

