6. RESEARCH QUESTION AND OBJECTIVES

This study is intended to assess the following items, etc. for the safety and effectiveness of Vfend 200 mg for Intravenous Use, Vfend Tablets 50 mg, Vfend Tablets 200 mg, and Vfend Dry Syrup 2800 mg (hereinafter referred to as this product) in daily clinical practice for invasive fungal infections in children and review the necessity for further special investigation and post-marketing clinical study.

- Unknown adverse reactions
- Occurrence of adverse reactions under actual clinical settings
- Factors considered to affect the safety and effectiveness of this product

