8.2.3.1. Adverse Drug Reactions

- **All adverse drug reactions**

The number and proportion of patients with adverse drug reactions will be tabulated by SOC and PT. Also by diagnostic name (name of infection), the number and proportion of patients with adverse drug reactions will be tabulated by SOC and PT.

- **Serious adverse drug reactions**

The number and proportion of patients with serious adverse drug reactions will be tabulated by SOC and PT. In addition, the number and proportion of patients by known/unknown serious adverse drug reactions will be tabulated by SOC and PT.

- **Details of adverse drug reactions**

The number and proportion of patients with adverse drug reactions will be tabulated by SOC and PT for each of the following items.

- Seriousness [serious, non-serious]
- Known/unknown [known, unknown]
- Intervention [discontinuation, temporarily discontinued, dose reduction]
- Outcome [not recovered, recovered with sequela, recovering, resolved/recovered, unknown]

In addition, the number and proportion of patients with adverse drug reactions meeting all of the following conditions will be tabulated by SOC and PT.

- Seriousness is “non-serious”
- Intervention is “discontinuation,” “temporarily discontinued,” or “dose reduction”
- Outcome is “not recovered” or “recovered with sequela”

If the same adverse event (the same PT) occurs more than once in the same patient, it will be handled as follows in the tabulation of the number of patients with events:

- Seriousness: If both serious and non-serious events are reported, “serious” will be adopted.
- Known/unknown: If both known and unknown events are reported, “unknown” will be adopted.
- Number of days to onset: The number of days to the first event will be adopted.
- Intervention: If multiple types of action taken with Vfend for the adverse events are reported, one of discontinuation, temporarily discontinued, dose reduction, or none, in descending order of precedence, will be adopted.
- Outcome: The outcome of the last occurring event will be used.

- **Safety specifications**

The number and proportion of patients with events will be tabulated. In addition, the number and proportion of patients with safety specifications by intervention and outcome will be tabulated by SOC and PT.

- **Major investigation items**

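### SAP 8.2.3.5 commits to a reaction-level tabulation by factor, then makes its reporting depend on an undefined judgement of the result

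*SAP*

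**What the plan says.** The protocol (Section 6) names as an objective: "Factors considered to affect the safety and effectiveness of this product". The SAP serves the safety half of this in three places.

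- **8.2.3.4 (Subgroup Analysis):** the main commitment reads: "The number and proportion of patients who experienced at least one adverse drug reaction will be tabulated for each factor specified in Section 5.4". Risk ratios and risk differences with 95% confidence intervals follow under 8.1.3, and "The same analysis will be performed for serious adverse drug reactions". No reporting condition is attached.
- **8.2.3.1 (Adverse Drug Reactions):** "Also by diagnostic name (name of infection), the number and proportion of patients with adverse drug reactions will be tabulated by SOC and PT". A further SOC/PT tabulation is planned by use of contraindicated medications and of those requiring precautions. Neither has a reporting condition.
- **8.2.3.5 (Exploratory Analysis):** "The following exploratory analysis will be performed for factors affecting safety". The single item listed is that patients with ADRs "will be tabulated by SOC and PT by factor with a risk ratio of" at least 2 or at most 0.5. Then comes "An additional analysis may be performed as necessary", followed by "The exploratory analysis will be reported only when results giving important interpretation are obtained".

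The last two sentences recur in 8.2.4.5 for effectiveness, where no named analysis precedes them. SAP Section 3 promises that every specified analysis is carried out at the final analysis. It does not say that every one is reported.

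**The concern.** The subject of the conditional sentence in 8.2.3.5 repeats the noun that introduced the committed tabulation a few lines above. Read plainly, the condition covers that tabulation and not only the optional extras. A pre-specified analysis would then appear in the report or not according to its result, by a standard that the SAP leaves open.

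The table matters because 8.2.3.4 shows only whether a factor is associated with having any ADR or any serious ADR. It does not show which reaction drives the association. That step, from a raised risk ratio to a named reaction, is what 8.2.3.5 supplies. The amendment history gives it added weight: Version 3.0 removed the subgroup analyses of the major investigation items and of ADRs with at least 10% incidence, and Version 4.0 added this tabulation. If the table can be withheld, a reader who does not find it cannot tell an unremarkable pattern from an unreported one.

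**Working it through.** The plan states no figure on this point, so the check is mainly a comparison of passages, with one count and one illustration.

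**1. Which analyses the condition reaches**

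| SAP section | Analysis | Committed? | Reporting depends on result? |
|---|---|---|---|
| 8.2.3.4 | Any ADR and serious ADRs by each 5.4 factor | Yes | No |
| 8.2.3.1 | SOC/PT by diagnosis | Yes | No |
| 8.2.3.1 | SOC/PT by concomitant medication (contraindicated or precaution) | Yes | No |
| 8.2.4.4 | Clinical response by each 5.4 factor | Yes | No |
| 8.2.3.5 | SOC/PT for factors meeting the risk-ratio trigger | Yes | Yes, on the plain wording |
| 8.2.3.5, 8.2.4.5 | Unplanned additional analyses | No | Yes |

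Only one row is both committed and conditional.

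**2. How many factors depend on that row**

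Section 5.4 lists 14 background factors for safety. Two have an unconditional SOC/PT table elsewhere: diagnosis, and concomitant medications requiring precautions. That leaves 14 − 2 = 12: hepatic dysfunction, renal dysfunction, two age groupings, severity, fever unresponsive to antibacterials, concomitant antifungals, prior antifungals, treatment period, long-term treatment, first-day dose and mean maintenance dose. Concomitant antifungals may be partly covered if some are on the precaution list; the documents do not say. Section 5.4 also names special subgroups outside the 14. For one of them, contraindicated patients, 8.2.3.4 allows an SOC/PT tabulation if needed.

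**3. The trigger already selects on results (illustration)**

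I take the trigger to use the 8.2.3.4 risk ratios; 8.2.3.5 does not say so. For a two-level factor with no true association, group sizes n1 + n2 = 100 (the planned sample size) and a common event rate p, the chance of meeting the trigger is

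P = Σ Bin(a; n1, p) · Bin(b; n2, p), summed over all (a, b) with (a/n1)/(b/n2) ≥ 2 or ≤ 0.5,

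counting zero events in one group as meeting it and zero in both as not. The splits and the 10% rate are assumptions. The other two rates are those given in protocol 7.5.2 for hepatic toxicity (19.0%) and visual events (42.9%), borrowed only to set a range.

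| Split | p = 10% | p = 19% | p = 42.9% |
|---|---|---|---|
| 10/90 | 0.55 | 0.36 | 0.11 |
| 20/80 | 0.45 | 0.23 | 0.03 |
| 50/50 | 0.34 | 0.14 | 0.01 |

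For less common outcomes or uneven splits, chance alone often brings a factor to the PT-level stage. The condition on reporting is then a second, undefined selection on top of the first. The PT tables are what would help a reader judge whether a triggered factor shows a coherent pattern or scattered single cases.

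**The case against.** The strongest reply is that the sentence was meant for optional work only. It directly follows the sentence allowing additional analyses, and in 8.2.4.5 the same pair of sentences can refer to nothing else. That reading is plausible and may be what the sponsor intended. The text of 8.2.3.5 does not say so, however, and its wording points back to the named analysis. If the narrow reading is right, stating it costs nothing.

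A second reply is that little is hidden. The factors and levels are fixed in Section 5.4, the 8.2.3.4 results are unconditional, and a factor that crossed 2 or 0.5 without a PT table would be visible as a gap. This largely stands, and it limits the point. The reader would see that a table is missing, but not what it contained.

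Two stronger inferences are tempting, and the documents do not support them:

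- **That all factor findings are selected on their results.** A reader might count the levels in Section 5.4, double the count for any and serious ADRs, and expect a number of chance findings to be reported with no denominator. Those comparisons belong to 8.2.3.4, which is tabulated in full, so the denominator is there. The trigger is also a risk-ratio size and not a significance test, and SAP 4.1 sets no significance level, so no fixed false-positive rate applies.
- **That this is the SAP's only PT-level analysis by factor.** Section 8.2.3.1 has unconditional ones by diagnosis and by concomitant medication.

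**Conclusion.** The point holds within a narrow scope. One committed table, which is the only planned PT-level tabulation by factor for 12 of 14 background factors, is reported only if its result is judged important, with no criterion. Unplanned additional analyses under 8.2.3.5 and 8.2.4.5 are subject to the same condition. In 8.2.4.5 no committed analysis is at risk.

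The conclusion rests on the plain reading of the sentence in 8.2.3.5. On the narrower reading, only the listing of optional analyses remains to be settled. The chance-trigger figures are illustrative and depend on assumed rates and splits; the conclusion does not need them. No sample-size or precision figure changes. The study is declared non-confirmatory, so this is a matter of transparent reporting on a stated objective. It should be corrected, but it does not threaten the main safety or effectiveness tables.

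**What to change.** In 8.2.3.5, state that the SOC/PT tabulation will always be reported for every factor meeting the risk-ratio trigger.

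In 8.2.3.5 and 8.2.4.5, replace the conditional sentence with a commitment along these lines: *Every additional analysis performed will be listed in the report, whatever its result.*

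The cost is a small SAP revision and a few more appendix pages. No new data, programming of new methods or change to the analysis sets is needed.

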8.2.4. Effectiveness Analysis

8.2.4.1. Clinical Response

In the clinical response analysis set, the number and proportion (clinical response rate) of patients for whom clinical response was determined as effective and the 95% confidence interval will be calculated. The formula to calculate the clinical response rate is shown below.

$$\text{Clinical response rate (\%)} = \frac{\text{the number of responders}}{\text{the number of patients in the clinical response analysis set excluding indeterminate patients}} \times 100$$

The clinical response rate will be calculated also by diagnostic name (name of infection) (definitive diagnosis + suspected cases) and by diagnostic name [definitive diagnosis] (name of infection).

8.2.4.2. Mycological Response

In the mycological analysis set, the number and proportion (eradication rate) of patients for whom mycological response was determined as eradication or presumed eradication and the

95% confidence interval will be calculated. The formula to calculate the eradication rate is shown below.

$$\text{Eradication rate (\%)} = \frac{\text{the number of patients with mycological eradication + presumed eradication}}{\text{the number of patients in the mycological analysis set excluding indeterminate patients}} \times 100$$

The eradication rate will be calculated also by diagnostic name (name of infection) (definitive diagnosis + suspected cases) and by diagnostic name [definitive diagnosis] (name of infection).

8.2.4.3. Mycological response by Causative Fungus

The number and proportion (eradication rate) of fungus for which eradication after treatment with Vfend was determined as eradication and the 95% confidence interval will be calculated by causative fungus identified at the initiation of treatment. The formula to calculate the eradication rate is shown below.

$$\text{Eradication rate by causative fungi (\%)} = \frac{\text{the number of eradicated fungi}}{\text{the number of (eradicated + persistent) fungi}} \times 100$$

8.2.4.4. Subgroup Analysis

For each factor specified in Section 5.4, subgroup analyses of clinical response will be performed.

8.2.4.5. Exploratory Analysis

An additional analysis may be performed as necessary. The exploratory analysis will be reported only when results giving important interpretation are obtained.

9. LISTINGS

The following listings will be prepared. Listings with [Intext] specified after the table name are in a format which allows attachment to the report without change.

- Listing of patients^a

^a : Estimated creatinine clearance in the listing will be calculated from serum creatinine before the initiation of Vfend treatment using the Cockcroft-Gault Cr calculation formula. eGFR will also be calculated because the CDK guideline for children recommends calculation of eGFR. A quintic equation will be used for calculation of

-
- Listing of patients with adverse events (including events observed after the observation period and follow-up period)
 - Listing of patients with adverse drug reactions
 - Listing of patients with adverse drug reactions among patients excluded from the safety analysis set
 - Listing of patients with serious adverse drug reactions [Intext]
 - List of events corresponding to safety specifications including major investigation items
 - List of adverse drug reactions falling under safety specifications including major investigation items [Intext]
 - Listing of other reasons for discontinuation [Intext]
 - Listing of mycological test
 - Listing of laboratory values
 - Listing of serological test and imaging test
 - Listing of the record of administration of Vfend and plasma voriconazole concentration
 - Listing of prior medications (antifungal agents) by patient
 - Listing of concomitant medications by patient [Intext]
 - Listing of deaths [Intext]

Furthermore, the following tables corresponding to appendix tables for periodic safety report (PSUR) will be prepared:

- Appendix Form 16 (Overview of patients in post-marketing surveillance)
- Appendix Form 15 (List of development of adverse drug reactions and infections)
- Appendix Form 12 (Development of adverse drug reactions and infections in additional pharmacovigilance plan)

eGFR for children. (See Attachment 10.3) The quintic equation is for patients aged 2 to 19 years but will be used also in patients aged <2 years.

10.3. Appendix 3: Formulas to Calculate Estimated Creatinine Clearance and eGFR

- Cockcroft-Gault Ccr calculation formula

Male: $Ccr = \{(140 - \text{age}) \times \text{weight (kg)}\} / \{72 \times \text{serum creatinine (mg/dL)}\}$

Female: $Ccr = 0.85 \times \{(140 - \text{age}) \times \text{weight (kg)}\} / \{72 \times \text{serum creatinine (mg/dL)}\}$

- Quintic equation

See Page 13 of Guidance for Evaluation of Renal Function at Diagnosis of Pediatric Chronic Kidney Disease (Pediatric CKD)

1. Quintic equation (≥ 2 to < 19 years)

With height presented as Ht (m), the reference value of serum Cr will be calculated, and eGFR will be calculated based on the reference value.

$$eGFR(\text{mL}/\text{min}/1.73\text{m}^2) = 110.2 \times \frac{\text{Reference value of serum Cr (mg/dL)}}{\text{Observed value of serum Cr (mg/dL)}} + 2.93$$

<Reference value of serum Cr (mg/dL)>

Male: $-1.259 \text{ Ht}^5 + 7.815 \text{ Ht}^4 - 18.57 \text{ Ht}^3 + 21.39 \text{ Ht}^2 - 11.71 \text{ Ht} + 2.628$

Female: $-4.536 \text{ Ht}^5 + 27.16 \text{ Ht}^4 - 63.47 \text{ Ht}^3 + 72.43 \text{ Ht}^2 - 40.06 \text{ Ht} + 8.778$

Uemura O, et al. Clin Exp Nephrol 2013 : Epub ahead of print

Guidance for Evaluation of Renal Function at Diagnosis of Pediatric Chronic Kidney Disease (Pediatric CKD)

[Edition] 2013 Health Labour Sciences Research Grant for Refractory Disease Research Project (Refractory Disease Research Project)

Group to Elucidate the Natural History of Pediatric Chronic Kidney Disease Including Congenital Anomalies of the Kidney and Urinary Tract and Establish Treatment Methods for Early Diagnosis and Inhibition of Progression of Renal Failure (Japanese Pediatric CKD Research Group)

[Cooperation] Japan Pediatric Society, Japanese Society of Pediatric Urology, The Japanese Society for Pediatric Nephrology

<https://cdn.jsn.or.jp/academicinfo/report/201402.pdf>

[REDACTED]	[REDACTED]
------------	------------

[REDACTED]	[REDACTED]		
[REDACTED]	[REDACTED]	[REDACTED]	
[REDACTED]	[REDACTED]	[REDACTED]	[REDACTED]
[REDACTED]	[REDACTED]	[REDACTED]	[REDACTED]
[REDACTED]	[REDACTED]	[REDACTED]	[REDACTED]

[REDACTED]

[REDACTED]	[REDACTED]		
[REDACTED]	[REDACTED]	[REDACTED]	
[REDACTED]	[REDACTED]	[REDACTED]	[REDACTED]
[REDACTED]	PPD [REDACTED]	[REDACTED]	[REDACTED]
